1 INTRODUCTION

1.1 Preface

Coronary artery bypass grafting (CABG) is the most common major surgical procedure in the United States with over 300,000 cases performed each year. To restore blood flow to the heart, vascular conduits from another part of the body are procured to create a bypass around critically blocked coronary arteries. The left internal thoracic artery is the conduit of choice for CABG due to its superior long-term patency. However, almost all patients referred for CABG require additional grafts to provide complete revascularization. This necessitates the harvest of other vessels, most commonly the saphenous vein which is used almost ubiquitously in contemporary CABG with an average of two vein grafts per CABG procedure. In the last 10 years, endoscopic vein harvesting (EVH) has been recommended as the preferred method over the traditional open harvesting technique (OVH) for saphenous vein graft (SVG) harvesting because it provides a minimally invasive approach. However, more recent investigations indicate potential for reduced long-term bypass graft patency and worse clinical outcomes with EVH. The long-term impact of EVH on clinical outcomes has never been investigated on a large scale using a definitive, adequately powered, prospective Randomized Clinical Trial (RCT) with long-term follow-up. Results of the proposed study will fill a significant gap in existing knowledge regarding long-term outcomes for EVH in CABG, improving the quality of the care we provide to Veterans and more broadly to all patients undergoing coronary revascularization. Findings from this study have the potential to significantly impact the VA and national cardiac surgery coronary revascularization guidelines.

1.2 Goal of the analyses

The goal is to investigate the impact of SVG harvesting technique (OVH vs. EVH) on MACE (major adverse cardiac events), a composite end point of all-cause mortality, nonfatal myocardial infarction and repeat revascularization, leg wound complication, patient satisfaction, and quality of life in addition to determining the role of vein harvester's experience on clinical outcomes.

2 STUDY OBJECTIVES AND ENDPOINTS

2.1 Study Objectives and Hypotheses

Primary Objectives:

Objective 1: To investigate the impact of SVG harvesting techniques – OVH vs. EVH on MACE, a composite end point of all-cause mortality, nonfatal myocardial infarction and repeat revascularization, over the active follow-up period of the study postoperatively.

Hypothesis 1: A significantly smaller proportion of CABG subjects with SVGs harvested by open technique will experience MACE post-surgery compared to CABG subjects with SVGs harvested by endoscopic technique during the active follow-up period.

Secondary Objectives:

Objective 2: To investigate the impact of SVG harvesting techniques – OVH vs. EVH on MACE, a composite endpoint of all-cause mortality, nonfatal myocardial infarction and repeat revascularization, at one and three-year postoperatively.

Hypothesis 2: One-year composite MACE rate will be 6 percentage points lower in the open harvesting group and three-year composite MACE rates will be at least 8-10 percentage points lower in the open vein harvesting group compared to the endoscopic vein harvesting group.

Objective 3: To investigate the impact of SVG harvesting techniques – OVH vs. EVH on MACE, a composite endpoint of all-cause mortality, nonfatal myocardial infarction and repeat revascularization, over the entire follow-up period (active and passive) of the study postoperatively.

Hypothesis 3: A significant smaller proportion of CABG subjects with SVGs harvested by open technique will experience MACE post-surgery compared to CABG subjects with SVGs harvested by endoscopic technique during the entire follow-up period.

Tertiary Objectives:

Objective 4: Investigate the impact of the two harvesting techniques - open vs. endoscopic - on clinical indicators of leg wound complications and subject satisfaction at six weeks post-surgery.

Hypothesis 4: Leg wound complications will be lower and satisfaction will be higher in the EVH group compared to OVH group.

Objective 5: Compare subject quality of life scores according to the SVG harvest technique at six weeks post-surgery.

Hypothesis 5: Subjects' quality of life scores will be higher in the EVH group compared to the OVH group.

Objective 6: Determine the role of vein harvester experience on clinical outcomes.

Exploratory Aim with no hypothesis specified.

2.2 Endpoints

2.2.1 Primary Outcome Measures

The primary outcome measure is MACE following randomization and the index CABG.

For hypothesis 1: The outcome measure, MACE (major adverse cardiac events) is a composite endpoint that includes death (all-cause), myocardial infarction (MI), and revascularization for myocardial ischemia. Each randomized participant (either in EVH or OVH) will be followed after the index CABG to capture the time-to-MACE event where an ‘EVENT’ will be defined as either death (all-cause) or an MI or a revascularization procedure during the follow-up period. Total follow-up period will be 6.5 years of which the first 4.5 years will be active follow-up (using in-clinic visit or by telephone) period and will be carried out by the site personnel. The remaining 2 years will be passive follow-up which will be carried out centrally by the chair’s office staff using VA clinical and administrative databases (CPRS, VASQIP, etc.). A minimum of 1 year of active follow-up will be used for participants who will be randomized at the tail end of the 3-year projected enrollment period of the study. The participants who will either be lost to follow-up or will not experience an ‘EVENT’ before the end of the follow-up period will be considered as right-censored. The primary analysis of such time-to-Mace event data will include the events only from the active follow-up period (which is approximately 4.5 years).

2.2.2 Secondary and Tertiary Outcome Measures

Secondary outcomes include MACE at one and three-year and over the entire follow-up period (active and passive) of the study postoperatively. Tertiary outcomes include leg wound complication and quality of life.

For hypothesis 2: MACE at one and three-year postoperatively.

For hypothesis 3: MACE over the entire follow-up period (active and passive) of the study postoperatively.

For hypothesis 4: Assessment of leg wound complications will be assessed at the time of discharge and at approximately six-week post-surgery during a clinic visit (this visit will take place between approximately 4 to 8 weeks post-surgery). Post-operative leg wound complication status (yes/no) will be determined based on these assessments.

For hypothesis 5: The Quality of Life (QoL) outcome measure will be the summary measures from the VR-12 instrument of health related quality of life as measured by the Physical Component Summary (PCS) and Mental Component Summary (MCS) and the Seattle Angina Questionnaire. QoL self-assessments will be completed at baseline, six weeks, and one year (by mail or telephone). Additionally, participants will be categorized as “improved”, “no change”, or “worsened” based on their baseline scores.

For hypothesis 6: Clinical measures include MACE.

2.3 Derived variables

2.3.1 Seattle Angina Questionnaire

The Seattle Angina Questionnaire (SAQ) is the leading health-related QoL measure for patients with coronary artery disease. The self-assessment questionnaire consists of a list of activities people often do during the week (e.g., dressing yourself, walking indoors on level ground, showering) and asks participants the amount of limitation (ranging from not at all limited to extremely limited) they have doing these activities due to chest pain, chest tightness, or angina over the previous 4 weeks. Additional questions ask about frequency and treatment of chest pain, chest tightness, or angina.

The answers provided on the SAQ are used to calculate scores in five scales: 1) Angina Stability, a measure of whether a patient's symptoms are changing over time; 2) Angina Frequency, a measure of how often a patient is having symptoms now; 3) Physical Limitation, a measure of how much a patient's condition is hampering his ability to do what he wants to do; 4) Treatment Satisfaction, a measure of well a patient understands her care and what she thinks of it; and 5) Quality of Life, a measure of the overall impact of a patient's condition on a patient's interpersonal relationships and state of mind. Participants will complete the SAQ at baseline, 6 weeks, and 1 year post-surgery. Higher scores are better. For follow-up assessments, participants will be categorized as "improved", "no change", or "worsened" based on their baseline scores.

2.3.2 VR-12

The Veterans RAND 12 Item Health Survey (VR-12) is a self-administered questionnaire with both physical and psychological domains using no more than 10 questions to create physical (PCS) and mental (MCS) component summary scores. The scoring of the PCS and MCS for the VR-12 is based on weights derived from the VR-36 instrument administered to 1.4 million Veteran enrollees with 877,775 respondents in the 1999 Large Health Survey of Veteran Enrollees (Veterans Health Study) (Iqbal et al. 2009). Higher PCS and MCS scores reflect greater quality of life. Imputation methods will be used to calculate scores for Veterans who do not complete all 12 questions included in this measure. Participants will complete the VR-12 at baseline, 6 weeks, and 1 year post-surgery. For follow-up assessments, change from baseline will be examined. Higher PCS and MCS scores reflect greater quality of life.

2.3.3 Syntax Score

The SYNTAX Score is a unique tool to score the complexity of coronary artery disease (available at www.syntaxscore.com). Higher scores are associated with greater risk.

2.3.4 VASQIP Score

The VA Surgical Quality Improvement Program (VASQIP) score will be used to assess 30-day surgical risk of mortality. Higher scores are associated with greater risk.

2.3.5 STS Score

The Society of Thoracic Surgeons (STS) score will be used to assess risk of operative mortality and morbidity of adult cardiac surgery on the basis of patient demographic and clinical characteristics. Higher scores are associated with greater risk.

2.3.6 Leg Incision Pain Impact Questionnaire

Severe leg pain, due to incisions made during vein grafting, data will be collected at discharge and at 4-6 weeks post-CABG. The Pain Impact Questionnaire (PIQ) is a 6-item measure of pain severity and its impact on health-related QoL (Becker et al. 2005). Impact scores range from 40 to 78 with higher scores reflecting greater pain impact. Scores can be grouped into: 1) Little or No Impact (impact score \leq 50); 2) Some Impact ($50 < \text{impact score} \leq 57$); 3) Substantial Impact ($57 < \text{impact score} \leq 63$); and 4) Severe Impact ($\text{impact score} > 63$). A pain severity rating is also calculated from the first PIQ item and ranges from 1 to 6, with severe pain defined as a score of 3 (mild) or above.

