Subjects who suffer any one of these three outcomes within the first year or in the first three years after the index CABG will be counted towards calculating the proportions of subjects with MACE (yes/no) in each harvesting technique group – subjects with endoscopic vein grafting or subjects with open vein grafting. Only the first event will be considered as the MACE event. These two proportions will be compared using a chi-square test.

Post-operative Leg Wound Complications: All subjects in both harvesting technique groups – EVH or OVH – will be examined for complications of the leg wound from harvesting at discharge and at six weeks post-surgery. Post-operative leg wound complication status (yes/no) will be recorded at discharge and at six weeks post-surgery. Proportion of subjects with leg wound complications will be computed for each treatment group and these proportions at each time point will be compared using chi-square tests. The impact of confounding variables, such as, BMI, diabetes status, smoking status, on the post-operative leg wound infection will be analyzed using a logistic regression.

Severity of Incisional Leg Pain: Severe leg pain, due to incisions made during vein grafting, data will be collected at discharge and at six-week post CABG. Proportion of subjects with severe pain (pain score 3 and above = yes) at each time point will be compared using chi-square statistics.

Quality of Life: QoL scores using VR-12 and Seattle Angina Questionnaire will be computed at baseline, six week, and 12 months post-surgery for the subjects in the two harvesting technique groups (EVH and OVH). Subjects in both groups will be categorized as "improved", "no change" and "worse" based on their baseline scores. The proportion of subjects in these three categories will be compared between the two groups using chi-square statistics. The actual scores from these measures will also be used to compare subjects in the two harvesting technique groups using analyses of covariance techniques, where the baseline (pre-surgery) scores will be used as a covariate.

E. Interim Monitoring

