Every effort will be made to minimize the occurrence of missing data, particularly for the primary and main secondary outcome measures. For the primary outcome (MACE), every effort will be made to contact the subjects over the phone every three months until subject termination. In the event of a potential drop out, every effort will be made to capture the MACE data from the VA databases.

H. Reporting of Any Deviations from the Original Statistical Plan

A more detailed statistical analysis plan (SAP) will be generated which will include the details of each statistical analysis plan for each outcome measure along with the suggested table shells for any reports that will be produced during the study and at the end of the study. Any deviations in the statistical plan from the protocol will be specified in the SAP. Any deviations from the SAP will be specified in the main manuscript which will be prepared and published at the end of the study.

XVIII. PUBLICATIONS

A. Publication Policy

It is the policy of the Cooperative Studies Program not to reveal outcome data to site investigators until the data collection phase of the study is complete. This policy is meant to prevent possible biases that might affect data collection. Members of the DMC will be reviewing outcome results to ensure that the study will be terminated early if a treatment is identified as prohibitively dangerous or if a definitive answer is reached prior to the scheduled study termination date.

All presentations and publications resulting from this study will follow CSP policy as specified by the CSP guidelines. The presentation or publication of any or all data collected by site investigators on subjects entered into a Department of Veterans Affairs Cooperative Study is under the direct control of the study's Executive Committee. No individual site investigator has the right to use the study's data to perform analyses or interpretations, or to make public presentations or seek publication of any or all of the data without specific approval of the Executive Committee.

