Table 18 provides the format in which the logistic regression analysis results for the leg wound healings complications will be presented. Each of the covariates in the model will be presented with individual odds ratio and 95% Confidence Interval.

Table 18: Logistic Regression Analysis of Leg Wound Healing Complications Data at 6-week Post Surgery

	Odds Ratio	95% Confidence Interval	
		LL	UL
Harvesting Technique			
BMI			
Harvester Experience			
Age of patient			
Diabetes Status			
Smoking Status			

4. **Severity of Incisional Leg Pain:** Severe leg pain, due to incisions made during vein grafting, data will be collected at discharge and at six-week post CABG. Proportion of patients with severe pain (pain score 3 and above = yes) at each time point will be compared using chi-square statistics.

The results from the chi-square analysis will be presented with counts of 'yes' and 'no' in regards to severity of incisional leg pain in the two harvesting techniques as shown in Table 19.

Table 19: Severity of Incisional Leg Pain distributions in harvesting technique groups

Harvesting Severity of Leg Pain	OVH	EVH	Total
No			
Yes			
Total			
ChiSq =	p-value =		

5. **Quality of Life:** QoL scores, from VR-12 and Seattle Angina Questionnaire, will be computed at baseline, six-weeks, and 12 months post-surgery for the patients in both harvesting technique groups (EVH and OVH). Patients in the two groups will be categorized as “improved”, “no change” and “worse” based on their baseline scores. The proportions of patients in these three categories will be compared between the two groups using chi-square statistics. The actual scores from these measures will also be used to compare patients in the two harvesting technique groups using analyses of covariance techniques, where the baseline (pre-surgery) scores will be used as a covariate. The results from the chi-square analysis will be presented with counts of ‘yes’ and ‘no’ in regards to QoL scores categorized as “improved”, “no change” and “worse” in the two harvesting techniques as shown in Table 20. Table 21 provides the format in which the results from ANCOVA analysis will be presented.

Table 20: QoL/SAQ score distributions in harvesting technique groups

Harvesting QoL score	OVH	EVH	Total
Improved			
No Change			
Worse			
ChiSq =	p-value =		

Table 21: QoL/SAQ Scores by Harvesting Technique

Treatment Group	QoL Score		
	N	Mean	Standard Error
Covariate	Estimate	Std. Error	t-statistics
Harvesting Technique			

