 year5. Discharge order > 7 days of initial CABG No Yes →

--	--

 month

--	--

 day

--	--	--	--

 year6. Creatinine (mg/dL)

--	--

 .

--	--

 month

--	--

 day

--	--	--	--

 year7. Potassium (mEq/L)

--	--

 .

--	--

 month

--	--

 day

--	--	--	--

 year8. White Blood Cell Count ($10^3/\text{mm}^3$)

--	--

 .

--	--

 month

--	--

 day

--	--	--	--

 year9. Hematocrit (%)

--	--

 .

--	--

 month

--	--

 day

--	--	--	--

 year

S.I. Signature _____

Date _____

SITE NO.	SUBJECT ID	ALPHA CODE	DATE OF ASSESSMENT		

	

	

	

	

	

			Month	Day	Year

FORM 08 – LEG INCISION PAIN IMPACT QUESTIONNAIRE - DISCHARGE ASSESSMENT1. How much leg incision pain have you had during the past week?

None	Very mild	Mild	Moderate	Severe	Very severe
					

2. During the past week, how much did leg incision pain interfere with your normal activity?

Not at all	A little bit	Moderately	Quite a lot	Extremely
				

3. In the past week, how much of the time did leg incision pain interfere with your enjoyment of life?

Never	Rarely	Sometimes	Very often	Always
				

4. In the past week, how often did leg incision pain make simple tasks hard to complete?

Never	Rarely	Sometimes	Very often	Always
				

5. In the past week, how often were your leisure activities affected by your leg incision pain (including exercise and hobbies)?

Never	Rarely	Sometimes	Very often	Always
				

6. In the past week, how often did leg incision pain make you feel fed up and frustrated?

Never	Rarely	Sometimes	Very often	Always
				

SITE NO.	SUBJECT ID	ALPHA CODE	DATE OF ASSESSMENT																					

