

 	 	 	

				

 	 	 	 	

					

 	 	 	 	

					

 	 	

			

 	 	

			

 	 	 	 	

				
			Month	Day	Year																			

FORM 09 – LEG INCISION PAIN IMPACT QUESTIONNAIRE

6-WEEK POSTOPERATIVE ASSESSMENT

1. How much leg incision pain have you had during the past 4 weeks?

None	Very mild	Mild	Moderate	Severe	Very severe
					

2. During the past 4 weeks, how much did leg incision pain interfere with your normal activity?

Not at all	A little bit	Moderately	Quite a lot	Extremely
				

3. In the past 4 weeks, how much of the time did leg incision pain interfere with your enjoyment of life?

Never	Rarely	Sometimes	Very often	Always
				

4. In the past 4 weeks, how often did leg incision pain make simple tasks hard to complete?

Never	Rarely	Sometimes	Very often	Always
				

5. In the past 4 weeks, how often were your leisure activities affected by your leg incision pain (including exercise and hobbies)?

Never	Rarely	Sometimes	Very often	Always
				

6. In the past 4 weeks, how often did leg incision pain make you feel fed up and frustrated?

Never	Rarely	Sometimes	Very often	Always
				

SITE NO.

--	--	--

SUBJECT ID

--	--	--	--

ALPHA CODE

--	--	--	--

9. Hospital stay prolonged >14 days: (if yes, complete Form 15 – SAE) No = 0 Yes=5

10. Development of pus as an outpatient: No = 0 Yes=5

11. Visiting nurse visit to dress wound: No = 0 Yes=5

12. **Asepsis Score Total > 10 INDICATES WOUND INFECTION**
(Total of Questions 1-11)

Score

--	--

S.I. Signature _____

Date _____

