7.3 Tertiary Outcomes

Tertiary objectives of this study include investigating the impact of SVG harvesting techniques – OVH vs. EVH on leg wound complication, patient satisfaction, and quality of life in addition to determining the role of vein harvester's experience on clinical outcomes.

All participants will be examined for post-operative complications of the leg wound from harvesting at discharge and at six weeks post-surgery. Post-operative leg wound complication status (yes-1/no-0) will be determined. The proportion of participants with leg wound complications will be computed for each treatment group and these proportions will be compared using Pearson's chi-square test (TABLE 27). The impact of confounding variables, such as BMI, diabetes status, and smoking status, on post-operative leg wound infection will be analyzed using multivariable logistic regression (TABLE 28). Surgical site infections at the vein harvest site according to the Center for Disease Control criteria will be explored.

Patient satisfaction will be assessed using the "Treatment Satisfaction" scale of the Seattle Angina Questionnaire. Participants will be categorized as "improved", "no change" and "worsened" at 6 weeks and 12 months compared to their baseline scores (TABLE 29). The proportion of participants in these three categories will be compared between the two groups using Pearson's chi-square test. The actual scores from these measures will also be used to compare harvesting techniques using analysis of covariance (ANCOVA) techniques, where the baseline (pre-surgery) scores will be used as a covariate (TABLE 30).

The occurrence of severe leg pain, due to incisions made during vein grafting, will be collected at discharge and 4-6 weeks post-CABG. The proportion of participants with severe pain (yes = pain severity rating score ≥ 3) at each time point will be compared across groups using Pearson's chi-square test (TABLE 31).

Quality of life scores using the PCS and MCS of the VR-12 and the "Quality of Life" scale of the Seattle Angina Questionnaire will be computed at baseline, six weeks, and 12 months post-surgery for participants in each SVG harvesting group. For each component of the VR-12 (PCS and MCS), mean changes from baseline at six weeks and 12 months will be computed and compared using ANCOVA (TABLE 32).

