Center	Rate of Reporting	Participant ID	Protocol Non-Compliance Code	Date of Deviation
Albuquerque (501)				
...				
... and so on				

FIGURE 2: Kaplan-Meier Survival Curves

[figure not shown]

TABLE 25: MACE, Active Follow-up: Results of Multivariable Cox Proportional Hazards Regression Model

Parameter	DF	Parameter Estimate	Standard Error	Chi-Square Test Statistic	p-value	Hazard Ratio	95% Hazard CI
EVH (vs. OVH)							
Covariate 1							
...							
... and so on							

TABLE 26: Major Adverse Cardiac Events at 1-year and 3-year, by Treatment

		OVH		EVH		Total		p-value
		N	%	N	%	N	%	
1-Year	MACE							
	Death							----
	MI							----
	RR							----
3-Year	MACE							
	Death							----
	MI							----
	RR							----

TABLE 27: Leg Incision Healing by Treatment

	OVH		EVH		Total		p-value
	N	%	N	%	N	%	
No Disturbance							----
Complication (Any Disturbance)							

TABLE 28: Leg Incision Healing by Treatment: Results of Multivariable Logistic Regression Model

Parameter	DF	Parameter Estimate	Standard Error	Chi-Square Test Statistic	p-value	Odds Ratio	95% CI
EVH (vs. OVH)							
Covariate 1							
...							
... and so on							

TABLE 29: Seattle Angina Questionnaire: Change from Baseline by Treatment

			OVH		EVH		Total		p-value
			N	%	N	%	N	%	
[Component scale]	6-week	Improved							
		No Change							----
		Worsened							-----
	12-month	Improved							
		No Change							----
		Worsened							-----

* No change = (mean score change < 5)

TABLE 30: Seattle Angina Questionnaire: Results of ANCOVA Model

		Parameter	DF	Parameter Estimate	Standard Error	t-Test Statistic	p-value
[Component scale]	[6-week /12-month]	Intercept					
		Baseline Score					
		EVH (vs. OVH)					
		Interaction (if needed)					

TABLE 31: Impact and Severity of Incisional Leg Pain at by Treatment

		OVH		EVH		Total		p-value
		N	%	N	%	N	%	
Discharge	Little or no impact (impact score ≤ 50)							
	Some impact ($50 < \text{impact score} \leq 57$)							----
	Substantial impact ($57 < \text{impact score} \leq 63$)							----
	Severe impact (impact score > 63)							----
	Severe (per severity rating) (Score of 3 or above)							
6-Weeks	Little or no impact (impact score ≤ 50)							
	Some impact ($50 < \text{impact score} \leq 57$)							----
	Substantial impact ($57 < \text{impact score} \leq 63$)							----
	Severe impact (impact score > 63)							----
	Severe (per severity rating) (Score of 3 or above)							

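### The SAP counts every leg-pain answer from Mild upward as severe pain, so the reported severe-pain rate will be too high in both arms

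*SAP*

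**What the plan says.** SAP 2.3.6 derives a pain severity rating from item 1 of the Pain Impact Questionnaire. The rating "ranges from 1 to 6, with severe pain defined as a score of 3 (mild) or above".

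The rule is carried into the analysis and the report:

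- **SAP 7.3** compares "The proportion of participants with severe pain (yes = pain severity rating score ≥ 3) at each time point" between the arms with Pearson's chi-square test.
- **SAP Table 31** has a row at discharge and another at six weeks labelled "Severe (per severity rating) (Score of 3 or above").

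The label and cut come from the protocol. Section XVII.D.3 states: "Proportion of subjects with severe pain (pain score 3 and above = yes) at each time point will be compared using chi-square statistics". Appendix D repeats this almost word for word. Neither place names the questionnaire item or says how its answers are coded.

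The item is printed in the protocol's data forms. Form 08 (discharge) asks "How much leg incision pain have you had during the past week"; Form 09 (six weeks) asks "How much leg incision pain have you had during the past 4 weeks". Both offer the same six ordered answers: None, Very mild, Mild, Moderate, Severe, Very severe.

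**The concern.** The SAP definition contradicts itself: it identifies score 3 as mild and classes it as severe in the same sentence. Patients who tick Mild or Moderate would be reported as having severe pain.

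The word matters more than the cut here. Harvest-site morbidity is one side of the trade-off between the two techniques; the protocol's background cites lower postoperative pain as a benefit of EVH, and section IV names pain among the harvest-site morbidity to be minimised. A published severe-pain percentage will be read as severe pain. Someone looking only at Table 31 cannot recover the meaning, because the row gives the number 3 but neither the coding nor the word mild.

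**Working it through.** **1. Coding.** SAP 2.3.6 gives a range of 1 to 6 and equates 3 with mild. Applied to the six ordered answers on Forms 08 and 09:

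| Answer | Score | Counted as severe (3 or above) | Labelled severe on the form (5 or above) |
|---|---|---|---|
| None | 1 | no | no |
| Very mild | 2 | no | no |
| Mild | 3 | yes | no |
| Moderate | 4 | yes | no |
| Severe | 5 | yes | yes |
| Very severe | 6 | yes | yes |

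The SAP rule takes 4 of 6 answers; the form's own wording supports 2 of 6. A 0 to 5 coding would put 3 at Moderate, but the SAP's stated range and its gloss on score 3 rule that out.

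**2. Overstatement.** In each arm and at each time point,

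P(score ≥ 3) − P(score ≥ 5) = P(Mild) + P(Moderate).

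This is an identity and needs no distributional assumption.

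**3. Size in participants.** The planned total of 1150 gives 1150 / 2 = 575 per arm. Assume everyone answers item 1. The documents give no response shares, so a range is assumed for Mild plus Moderate:

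- 10%: 0.10 × 575 = 57.5, about 58 per arm
- 50%: 0.50 × 575 = 287.5, about 288 per arm

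As an illustration, take assumed shares from None to Very severe of 30, 25, 20, 15, 7 and 3%. The reported severe-pain rate would be 20 + 15 + 7 + 3 = 45%, against 7 + 3 = 10% answering Severe or Very severe. The difference is 35 points, equal to 20 + 15.

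**4. Does the cut cost power?** Two proportions, two-sided 0.05, n = 575 per arm, with

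power = Φ{ [ |p1 − p2| − 1.96 √(2 p̄(1 − p̄)/n) ] / √[ (p1(1 − p1) + p2(1 − p2))/n ] }, where p̄ is the mean of p1 and p2.

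All shares are assumed:

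| Where the effect lies | At 3 or above | At 5 or above |
|---|---|---|
| Severe and Very severe only, with 15% Mild or Moderate in both arms | 25% v 20%: power 0.53 | 10% v 5%: power 0.90 |
| Whole scale shifts | 45% v 35%: power 0.93 | 10% v 7%: power 0.45 |

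The ordering reverses between the two cases, so neither cut is generally more powerful. There is no power argument against the cut of 3.

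**The case against.** The strongest case on the other side has four parts.

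- **Nothing inferential changes.** The cut is pre-specified and the same in protocol and SAP. No hypothesis names pain: H4 covers wound complications and satisfaction, H5 quality of life. This is correct and limits the point to the label and the rate reported under it.
- **The definition is disclosed.** SAP 2.3.6 prints the word mild, so an analyst cannot program it wrongly, and Table 31 also reports graded impact categories, including a severe-impact row for scores above 63. But impact is a different construct from the item 1 rating. Its presence gives the table two meanings of severe and corrects neither.
- **The cut, not the label, might be the mistake.** The protocol does not settle this. The SAP explicitly ties 3 to mild and keeps the same cut throughout, so correcting the label is the less disruptive repair. It has a price: severe pain, the outcome the protocol names, would then be reported by arm but not tested.
- **The participant counts rest on assumptions.** This stands. Deaths and missed six-week visits will reduce the numbers answering, and SAP section 6 bases percentages on non-missing data. The identity in step 2 does not depend on those assumptions.

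**Conclusion.** The concern holds. Followed as written, the plan reports and tests as severe pain a category that starts at Mild. The reported rate is too high in each arm, at discharge and at six weeks, by the combined Mild and Moderate share. That share is unknown; over an assumed 10% to 50%, with 575 per arm all answering, it is about 58 to 288 participants per arm.

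The scope is narrow. The test at 3 or above is a valid comparison of at-least-mild pain. MACE, the sample size and the type I error rate are untouched, and no loss of power is claimed. The outcome is tertiary in the SAP, though the protocol lists it among its secondary measures. It should be corrected because the reported figure would be wrong as labelled.

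**What to change.** Change the SAP only, in 2.3.6, 7.3 and Table 31:

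1. Keep the cut of 3 or above and the chi-square test. Rename the outcome *at least mild pain (item 1, score 3 or above)*.
2. State the coding in 2.3.6: None = 1, Very mild = 2, Mild = 3, Moderate = 4, Severe = 5, Very severe = 6.
3. Add one descriptive row to Table 31, without a p-value: number and percentage answering Severe or Very severe (score 5 or above), by arm, at discharge and six weeks.
4. Record that the label now differs from protocol XVII.D.3 and Appendix D. Protocol XVII.H provides for this: "Any deviations in the statistical plan from the protocol will be specified in the SAP".

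The cost is SAP wording and one derived variable from data already collected. No protocol amendment is needed, and no test is added, so multiplicity does not change. The new row may hold few events, and the SAP should say plainly that the comparison at 5 or above is descriptive.
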